9.1.2 Censoring rules for Overall Survival (OS)

Comparison 1:

- Arm C subjects who have died or are known to be alive after ‘pooling cut-off date’ will be censored on the ‘pooling cut-off’ date. Refer to Section 4.5 for pooling cut-off date.
- All other subjects in arms A, B and C, refer to [Table 9–3](#) for censoring rules.
- Overall Survival (OS) following randomization = End Date – Date of Randomization +1

Comparison 2

- For Comparison 2 eligible subjects, refer to [Table 9-3](#) for censoring rules.
- Overall Survival (OS) following Week 24 baseline = End Date – Date of Week 24 baseline(the 6th dose date) +1

Table 9–3 Overall Survival censoring rules

Situation	End Date	Censored	Reason for Censoring
Death on or prior to database cut off date	Date of Death	No	N/A
Not known to have died as of database cut off date	Last known alive date (LKAD) on or prior to database cutoff	Yes	No Death
Lost to follow-up prior to database cutoff	Last known alive date (LKAD)	Yes	Lost to follow up

9.1.3 Censoring rules for other time-to-event endpoints

Comparison 1:

- Arm C subjects who had relevant event assessment or event after ‘pooling cut-off date’ will be censored on last assessment date prior to ‘pooling cut-off date’. Refer to Section 4.5 for pooling cut-off date.
- All other subjects in arms A, B and C, refer to
- [Table 9–4](#) for censoring rules.
- Randomization baseline is used for this comparison
- Time-to-event following randomization = End date - date of randomization +1

Comparison 2:

- Subjects who had a relevant event between date of randomization and Week 24 baseline will be censored at date of Week 24 baseline, with the reason ‘First event occurred between date of randomization and Week 24 baseline’.
- All other subjects refer to
- [Table 9–4](#).
- Week 24 baseline is used for this comparison for following endpoints: Time to first SSE and Time to Pain progression
- Randomization baseline is used for this comparison for exploratory endpoints :Time to ALP progression, time to PSA progression, time to increase in analgesic use and time to pain progression or increase in analgesic use.
- The assessment prior to treatment start is used as baseline for time to increase in physical symptoms of disease.
- Time-to-event following Week 24 baseline = End date - date of week 24 baseline +1.

[Table 9–4](#) applies to the following endpoints:

- **Time to First Symptomatic Skeletal Event**
- **Time to Pain Progression**
- **Time to ALP Progression**
- **Time to ALP Progression without 12-week Restriction**
- **Time to PSA Progression**
- **Time to PSA Progression without 12-week Restriction**
- **Time to Increase in Analgesic Use**
 - Requires Baseline WPS ≤ 7 for inclusion in analysis
- **Time to Pain progression or increase in analgesic use**
 - Requires Baseline WPS ≤ 7 for inclusion in analysis
 - The last assessment for censoring purposes refers to the latest date Pain Progression assessment. The earlier of the date of pain progression or increase in analgesic use is taken as the endpoint.
- **Time to increase in physical symptoms of disease following start of treatment based on FPSI-DRS-P**

Table 9–4 Time-to Event Censoring Rules

Situation	End Date	Censored	Reason for Censoring
No baseline assessment	Relevant Baseline Date	Yes	No baseline assessment.
No post baseline assessment	Relevant Baseline Date	Yes	No post-baseline assessment.
Subject had an event	Date of first event	No	N/A
No event by database cutoff	Last assessment prior to	Yes	No Event

	database cutoff		
--	-----------------	--	--

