4.5 Data Rules

4.5.1 Determining Baseline Values

This study has two distinct baselines for efficacy analyses, the randomization baseline and the Week 24 baseline.

Randomization baseline value for efficacy parameters: is defined as the last non-missing value on or before the date of randomization.

Week 24 baseline: Unless otherwise specified, the ‘Week 24 baseline’ is defined as the date of the 6th injection. This baseline is defined only for those subjects who are eligible for Comparison 2 analyses. That is, subjects who had received at least 6 injections.

Week 24 baseline value for efficacy parameters: Unless otherwise specified, the ‘Week 24 baseline value’ is defined as the last non-missing value on or before the date of the 6th injection.

Ideally, this visit would be the date of the 7th injection for Arm C subjects and expected 7th injection date for Arm A subjects. However, the end of treatment visit (30±7 days from last dose) for Arm A subjects could be missing due to consent withdrawal or happen out of visit window. Hence, there is no comparable visit for Arm A subjects that could be used as the expected 7th injection date.

To account for this and achieve comparability between the two arms, the 6th injection date is used as the reference date for Comparison 2 subjects. It should be noted that this could lead to a somewhat dilution of the treatment effect in Arm C due to an early reference date.

Baseline value for safety parameters: is defined as the last non-missing value on or before the date of first dose.

4.5.2 Pooling cut-off date for Arm C subjects in Comparison 1

For Comparison 1, Arm C subjects are planned to be pooled with Arm A subjects. This pooling will be done such a way that only comparable data from Arm C subject pooled. The following algorithm will be used to identify the cut-off date for pooling:

Arm C: Pooling cut-off date = $7*28 + \text{randomization date}$; for subjects that were randomized but not treated,
= $(7-x)*28 + \text{last dose date}$; for $1 \leq x \leq 6$,
= 7th dose date; for $x \geq 7$,
where x be the number of injections received.

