6.2.3.1.1 Exploratory endpoints

For all exploratory time-to-event endpoints, randomization baseline will be used for all the analyses unless otherwise specified. Week 24 baseline will not be defined for exploratory endpoints.

Radiological endpoints

Only central reviewer assessments will be analyzed for exploratory radiological endpoints.

Time to radiological bone progression is defined for each comparison as the time (days) from randomization date to the date of confirmed radiological bone progression. See [Table 9–5](#) in Appendix [9.1.4](#) for detailed censoring rules.

Time to radiological soft-tissue progression is defined as the time (days) from randomization date to the date of radiological soft tissue progression. See [Table 9–5](#) in Appendix [9.1.4](#) for detailed censoring rules.

Quantitated bone scan endpoints

Digitized images of whole body quantified technetium-99 bone scans will be evaluated by the central imaging reviewer using CAD system software using the method of Brown et al. (2012) [8], as described in the imaging charter. The central reviewer will use the CAD system software to evaluate each subject’s digitized whole body quantified technetium-99 scans at each timepoint. The reviewer will identify the bone pixels, and determine the area (cm²) and disease status (bone lesion, not bone lesion) associated with each bone pixel [8].

The analysis timepoints for the analysis of quantitative bone scan endpoints are randomization baseline, Week 8, 16, 24, and every 12 weeks thereafter.

For analyses reported by visit, nominal visit per CRF will be used.

Patient bone scan lesion area (BSLA) is defined for each subject at each assessment as the sum of the pixel areas (cm²) of the set of the whole body quantified technetium-99 bone scan imaging pixels identified as bone lesion, as determined by the central imaging reviewer using the CAD system software.

Patient bone scan timepoint response rate (week 8, 16 and week 24) For each comparison, patient bone scan timepoint response with respect to the randomization baseline will be assessed according to the following criteria in [Table 6–2](#):

Table 6–2 Patient Bone Scan Timepoint Response Criteria Following Randomization

Responder (R)	30% or greater resolution of the BSLA compared to baseline
Stable Disease (SD)	Not meeting the criteria for R, PD, or UE

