Time to total ALP progression is defined as the time (days) from randomization date to the date of first total ALP progression. A progression event is defined as $\geq 25\%$ increase from randomization baseline value, at least 12 weeks from baseline in subjects with no ALP decline from baseline; or $\geq 25\%$ increase above the nadir value, which is confirmed by a second consecutive value obtained 3 or more weeks later but within 9 weeks in subjects with an initial ALP decline from the baseline.

Time to total ALP progression without 12-week restriction is similar to the time to total ALP progression defined above except that 12-week rule is removed in subjects with no ALP decline from baseline.

See [Table 9–4](#) in Appendix [9.1.3](#) for detailed censoring rules.

Time to PSA progression is defined as the time (days) from randomization baseline to the date of first PSA progression. A progression event is defined as $\geq 25\%$ increase from randomization baseline value and an increase in absolute value of ≥ 2 ng/mL, at least 12 weeks from the applicable baseline in subjects with no PSA decline from baseline; or $\geq 25\%$ increase and an absolute increase of ≥ 2 ng/mL above the nadir value, which is confirmed by a second consecutive value obtained 3 or more weeks later but within 9 weeks in subjects with an initial PSA decline from the baseline.

Time to PSA progression without 12 week restriction is similar to the time to PSA progression defined above except that 12-week rule is removed in subjects with no PSA decline from baseline.

See

Table 9–4 in Appendix 9.1.3 for detailed censoring rules .

Analgesic Use and Related Endpoints

Analgesic use in this study will be captured via two methods:

- Analgesic concomitant medication case report form, where the physician records the analgesic medication prescribed to manage pain.
- 24 hour analgesic consumption case report form, in which all analgesic medication taken in the last 24 hours.

Data from both sources will be used to identify strength of each analgesic used by each subject at baseline and post-baseline visits. The amount of medication a subject actually took cannot be calculated due to only prescribed information is collected on the eCRF. Hence, only drug name will be used in identifying non-, weak- or strong- opioids for analgesics related analyses.

Analgesic names will be coded into standard terms using the World Health Organization Drug Dictionary (WHO-DD), Version 2005 Q3.

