9.1.4 Censoring rules for time to radiological progression

Note: ‘radiological’ in the tables refer to either ‘radiological soft tissue’ or ‘radiological bone’ as applicable to the endpoint.

Refer to Section 4.5.2 for pooling cut-off date.

Table 9–5 applies to:

- **Time to radiological progression following randomization**
- **Time to radiological bone progression following randomization and**
- **Time to radiological soft tissue progression following randomization.**

The following censoring rules will be used for both Comparison 1 and Comparison 2. Randomization baseline is used for all comparisons.

Table 9–5 Censoring for Time to Radiological Bone/Soft Tissue Progression following randomization

Situation	End Date	Censored	Reason for Censoring
No randomization baseline or post-randomization baseline radiological assessment	Date of randomization	Yes	No baseline or post-baseline assessment.
Subject died without prior radiological progression	Date of last radiological assessment before death	Yes	No progression before death or database cutoff
Subject survived without radiological progression as of database cutoff date	Date of last radiological assessment before data cutoff	Yes	Alive and no progression before database cutoff
Subject had a radiological assessment of PD (no two consecutive missed radiological assessments*)	Date of first PD	No	N/A
PD immediately after two or more consecutive missed radiological assessments*	Date of last radiological assessment before missed assessments	Yes	Missed two or more consecutive tumor assessments
Subject discontinuation from study for reasons other than PD	Last radiological assessment date	Yes	Subject discontinued from study due to a reason other than PD
Subjects discontinued from study due to PD, but no documented date of PD	Date of last radiological assessment	Yes	Subjects discontinued from study due to PD, but no documented date of PD
New non-protocol permitted systemic anti-cancer treatment started	Date of last radiological assessment before starting new systemic anti-cancer treatment	Yes	New anti-cancer treatment started

*Two consecutive missing radiological assessments are defined as the time interval between two consecutive radiological assessments is more than 28 weeks = $2 \times (12+2)$ week, where 12-week is scheduled frequency for tumor assessment and 2-week is protocol-allowed window.

Duration = End date – randomization date +1

There will be no Week 24 baseline censoring for Comparison 2.

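### SAP 9.1.3, Comparison 2: the bullet that censors earlier events at dose 6 conflicts with timing the exploratory endpoints from randomization and, applied as written, biases their Kaplan-Meier medians upward

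*SAP*

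**What the plan says.** Section 9.1.3 lists the Comparison 2 rules for the nine endpoints under Table 9–4. The first bullet reads: "Subjects who had a relevant event between date of randomization and Week 24 baseline will be censored at date of Week 24 baseline". It is not restricted to any endpoint. Only the remaining subjects are sent to Table 9–4, where an event counts at its own date. Section 4.5.1 fixes the Week 24 baseline: it "is defined as the date of the 6th injection".

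The same list in 9.1.3 divides the endpoints by time origin:
- Time to first SSE and time to pain progression start at the Week 24 baseline.
- For others: "Randomization baseline is used for this comparison for exploratory endpoints :Time to ALP progression, time to PSA progression", followed by increase in analgesic use, and pain progression or increase in analgesic use.
- Time to increase in physical symptoms (FPSI-DRS-P) takes its baseline before treatment start, and section 6.2.3.1.1 times it from treatment start.

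The only Comparison 2 duration formula in 9.1.3 is "Time-to-event following Week 24 baseline = End date - date of week 24 baseline +1".

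Section 6.2.3.1.1 says of the exploratory endpoints: "Week 24 baseline will not be defined for exploratory endpoints". Its definitions agree with that, for example "Time to total ALP progression is defined as the time (days) from randomization date to the date of first total ALP progression". For the radiological endpoints, which also run from randomization, section 9.1.4 says: "There will be no Week 24 baseline censoring for Comparison 2". Section 9.1.5 repeats this for rPFS.

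**The concern.** Censoring an earlier event at the Week 24 baseline is harmless when the clock starts there. End date minus start date plus 1 gives one day of follow-up, so the subject contributes almost nothing.

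When the clock starts at randomization, the same rule moves the end date forward from the true event to dose 6 and removes the event. A subject with PSA progression at week 12 would be analysed as progression-free to about week 20 and censored there. No event before dose 6 could ever be counted.

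Seven of the nine Table 9–4 endpoints are exposed: ALP progression and PSA progression, each with and without the 12-week restriction; increase in analgesic use; pain progression or increase in analgesic use; and FPSI-DRS-P deterioration, from treatment start. Sections 6.2.2.2 and 6.2.3.1.1 together call for Kaplan-Meier curves, medians and quartiles with 80% and 95% confidence intervals for these endpoints. Those summaries would be too favourable in both arms and could not be set beside the Comparison 1 results for the same endpoints.

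**Working it through.** **1. The texts side by side.** The 9.1.3 bullet censors at dose 6 without naming an endpoint. Section 6.2.3.1.1 defines no Week 24 baseline for exploratory endpoints. Sections 9.1.4 and 9.1.5 switch Week 24 censoring off for the other randomization-timed endpoints, and 9.1.3 has no such line. It also has no Comparison 2 formula from randomization or treatment start. Table 7–1 records that the exploratory endpoints moved to the randomization baseline only in V2.0, which suggests that the bullet was left over.

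**2. The plan's own figure.** The SAP states no median or early-event rate for these endpoints, so the size of the shift has no counterpart to reproduce. The one related figure is the Comparison 2 power for SSE-FS (section 3.4). With 74.91 events, hazard ratio 0.606, 1:1 allocation and one-sided 0.10: √74.91 × 0.5009 / 2 − 1.2816 = 0.886, so power is 81.2%, against 80.6% stated. The design inputs are read correctly.

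**3. Time of dose 6.** With 4-weekly dosing, an undelayed dose 6 falls 5 × 4 = 20 weeks after dose 1 (no gap from randomization to dose 1 assumed).

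**4. Shift in the median.** Assume Weibull event times with true median m and shape k, and that all subjects reach dose 6 whether or not they have had the event. Under the literal rule survival is 1.0 to week 20 and then follows S(t)/S(20). The reported median is therefore m × [1 + (20/m)^k]^(1/k). For k = 1 (constant hazard) this is m + 20.

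| True median (weeks) | k = 0.7 | k = 1 | k = 1.5 | k = 2 |
|---|---|---|---|---|
| 12 | 42.7 (+30.7) | 32 (+20) | 25.8 (+13.8) | 23.3 (+11.3) |
| 24 | 59.1 (+35.1) | 44 (+20) | 35.0 (+11.0) | 31.2 (+7.2) |
| 39.1 | 78.3 (+39.2) | 59.1 (+20) | 48.1 (+9.0) | 43.9 (+4.8) |
| 52 | 93.9 (+41.9) | 72 (+20) | 60.0 (+8.0) | 55.7 (+3.7) |

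Simulation with 200,000 event times agrees to within rounding and sampling error. Under constant hazard, with dose 6 at weeks 20 to 28 (assumed delays), the shift is about 23 to 25 weeks.

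**5. Effect on the comparison.** Borrow the SAP's delayed-effect form from section 3.4 as an illustration: Arm A median 39.1 weeks (9 months), Arm C hazard multiplied by 0.606 after week 24.
- Arm A: true median 39.1; recoded 39.1 + 20 = 59.1, a shift of 20 weeks.
- Arm C: true median 24 + (39.1 − 24)/0.606 = 48.9. Recoded, 4 weeks of the 39.1 are used between weeks 20 and 24, so 24 + (39.1 − 4)/0.606 = 81.9, a shift of 33 weeks.
- Simulated Cox hazard ratio: 0.75 with true event dates, 0.63 with recoding, close to the post-change value of 0.606. The first figure varies by a few hundredths with the censoring pattern.

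**The case against.** The strongest reply is that the bullet was never meant for these endpoints. Section 6.2.3.1.1 and Table 7–1 both say that the Week 24 baseline is not used for them, the only Comparison 2 formula in 9.1.3 fits only the two Week 24 endpoints, and imaging shows the sponsor's intent. This is plausible, and it means that the documents do not establish that early events will be recoded. But dose 6 is a defined date for every subject in the Week 24 set, so the bullet can be programmed as written, and two programmers could produce different tables. The contradiction stands.

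Second, a reader might infer a fixed inflation of 20 weeks. The documents do not support that. It needs constant hazard and an undelayed dose 6, while the SAP gives no hazard for these endpoints and allows delays. For ALP and PSA, progression in subjects without a decline counts only from 12 weeks after baseline. That limits early events in those subjects under the restricted definitions and makes constant hazard a poor description of them.

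Third, a reader might infer that the log-rank test is untouched because both arms are recoded alike, or that it is invalid. Neither follows. Treatment is planned to be identical before dose 6, so discarding earlier events gives roughly a landmark comparison at dose 6. That is a legitimate contrast, but a different one, and the hazard ratio can change.

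Finally, these endpoints are exploratory. That is correct, and it limits the weight of the point.

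**Conclusion.** The point holds as an internal contradiction with a predictable consequence. The 9.1.3 bullet conflicts with the randomization timing of the exploratory endpoints, with section 6.2.3.1.1, and with the treatment of imaging in 9.1.4 and 9.1.5. If it is applied as written, Kaplan-Meier medians and quartiles are biased upward whenever events occur before dose 6.

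The direction does not depend on the hazard shape, but the size does: about 20 weeks under constant hazard with dose 6 at week 20, and roughly 4 to 42 weeks over Weibull shapes 2 to 0.7 and medians of 12 to 52 weeks. All of these shapes and medians are assumptions. In the delayed-effect illustration the hazard ratio moves from 0.75 to 0.63.

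The primary analysis has its own rules in 9.1.1 and starts at dose 6 for Comparison 2, so it is not affected. Time to first SSE and time to pain progression gain no event-free time either. The SAP should be corrected, but no primary conclusion depends on it.

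**What to change.** In section 9.1.3, Comparison 2:
- Limit the first bullet to time to first SSE and time to pain progression.
- For the other seven Table 9–4 endpoints, state, as for imaging, that no Week 24 baseline censoring applies and that each event counts at its own date.
- Add the duration formula: end date minus randomization date plus 1, and for FPSI-DRS-P end date minus treatment start date plus 1.

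This keeps the randomization-timed definitions already in the SAP. A landmark analysis from dose 6 in subjects event-free at that date may be added as a supplement, labelled as such. The cost is a few sentences in the appendix and a small programming change; no new data are needed.

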9.1.4 Censoring rules for time to radiological progression

Note: ‘radiological’ in the tables refer to either ‘radiological soft tissue’ or ‘radiological bone’ as applicable to the endpoint.

Refer to Section 4.5.2 for pooling cut-off date.

Table 9–5 applies to:

- **Time to radiological progression following randomization**
- **Time to radiological bone progression following randomization and**
- **Time to radiological soft tissue progression following randomization.**

The following censoring rules will be used for both Comparison 1 and Comparison 2. Randomization baseline is used for all comparisons.

Table 9–5 Censoring for Time to Radiological Bone/Soft Tissue Progression following randomization

Situation	End Date	Censored	Reason for Censoring
No randomization baseline or post-randomization baseline radiological assessment	Date of randomization	Yes	No baseline or post-baseline assessment.
Subject died without prior radiological progression	Date of last radiological assessment before death	Yes	No progression before death or database cutoff
Subject survived without radiological progression as of database cutoff date	Date of last radiological assessment before data cutoff	Yes	Alive and no progression before database cutoff
Subject had a radiological assessment of PD (no two consecutive missed radiological assessments*)	Date of first PD	No	N/A
PD immediately after two or more consecutive missed radiological assessments*	Date of last radiological assessment before missed assessments	Yes	Missed two or more consecutive tumor assessments
Subject discontinuation from study for reasons other than PD	Last radiological assessment date	Yes	Subject discontinued from study due to a reason other than PD
Subjects discontinued from study due to PD, but no documented date of PD	Date of last radiological assessment	Yes	Subjects discontinued from study due to PD, but no documented date of PD
New non-protocol permitted systemic anti-cancer treatment started	Date of last radiological assessment before starting new systemic anti-cancer treatment	Yes	New anti-cancer treatment started

*Two consecutive missing radiological assessments are defined as the time interval between two consecutive radiological assessments is more than 28 weeks = $2 \times (12+2)$ week, where 12-week is scheduled frequency for tumor assessment and 2-week is protocol-allowed window.

Duration = End date – randomization date +1

There will be no Week 24 baseline censoring for Comparison 2.

In addition to the rules in [Table 9–5](#) the following rule will be applied to Comparison 1:

Situation	End Date	Censored	Reason for Censoring
Arm C subject with no radiological progression event on or after pooling cutoff date	Last radiological progression assessment on or before pooling cutoff date	Yes	Post Week 24 Arm C events censored at pooling cutoff date

When determining time to radiographic progression, the following rules will be applied by taking into consideration of both bone and non-bone disease status:

Table 9–6 Censoring for Time to Radiological Progression Following Randomization

Situation		Event/Censor	Event/censor date	Combined Non-bone and Bone outcome
1	Bone	Event (PD)	Bone scan date	Event at min(Bone scan date, Non-Bone assessment date)Event at min(Bone scan date, Non-Bone assessment)
	Non-Bone	Event (PD)	Non-Bone assessment date	
2	Bone	Censor	Bone scan date	Censor at min(Non-Bone assessment date, Bone scan date)
	Non-Bone	Censor	Non-Bone assessment date	
3	Bone	Censor	Bone scan date	Event at Non-Bone assessment date: if Non-Bone assessment date \leq Bone scan date ; Else if Non-Bone assessment date $>$ Bone scan date AND Difference $<$ 28weeks; Else censor at bone scan Date; Event at Non-Bone assessment Date: if Non-Bone assessment Date \leq Bone scan date Else if Non-Bone assessment Date $>$ Bone scan date AND Difference $<$ 28weeks Else censor at bscan Date
	Non-Bone	Event(PD)	Non-Bone assessment date	
4	Bone	Event(PD)	Bone scan date	Event at bone scan date: if Bone scan date \leq Non-Bone assessment date Else if Bone scan date $>$ Non-Bone assessment date AND Difference $<$ 28weeks; Else censor at Non-Bone assessment date
	Non-Bone	Censor	Non-Bone assessment date	

